Chronic kidney disease (CKD) is a global public health problem. African Americans have a higher prevalence of late stage CKD than Whites and progress from early stage to late stage at a much more rapid rate. Biomedical explanations for African Americans' faster CKD progression prevail, with virtually no research attention paid to the role of social factors. Stress related to discrimination is a particularly compelling area of study in light of strong evidence demonstrating its linkages to CKD risk factors such as hypertension, diabetes, and obesity. The proposed proof of concept study will recruit 100 African American patients (both with and without diagnosed CKD) to determine whether discriminatory stressors are an important risk factor for CKD-related physiological processes and kidney functioning.

The long-term goal of this research program is to understand the impact of and pathways through which discriminatory stress contributes to CKD progression. The overall objective of this R21 application, which is the first step towards attainment of this long-term goal, is to obtain effect sizes for a larger prospective R01 and explore two hypothesized pathways (i.e., blood pressure reactivity and pathophysiological mechanisms) using a multi-method research design. This study will carry out the following specific aims:

1. **To examine associations between chronic stressors (i.e., discriminatory versus general), pathophysiological mechanisms (i.e., elevated inflammation and nocturnal blood pressure), and poor kidney functioning among 100 African American patients.**
 - a. Based on a cross-sectional research design, we hypothesize that chronic discriminatory stressors will be associated with poor kidney functioning independent of other chronic stressors as mediated by CKD-related inflammatory biomarkers and autonomic arousal.

2. **To examine the impact of acute stressors (i.e., discriminatory versus general) on short-term changes in CKD-related physiological processes (i.e., increases in inflammatory markers and blood pressure reactivity) in patients from aim 1.**
 - a. Based on an experimental research design, we hypothesize that discriminatory stressors will be more physiologically impactful than general stressors. Outcomes include several critical CKD-related inflammatory biomarkers and blood pressure reactivity assessed at three time points during the experimental manipulation.

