stressors often co-occur with other chronic stressors (e.g., financial stress, occupational stress, relationship stress, and parental stress) in African Americans, we will also determine whether discriminatory stressors are independent of these other types of stress. The long-term goal of this research program is to understand the impact of and pathways through which discriminatory stress contributes to CKD progression. The overall objective of this R21 research project, which is the first step towards attainment of this long-term goal, is to obtain effect sizes for a larger prospective R01 and explore two of the pathways hypothesized by Bruce et al. (i.e., blood pressure reactivity and pathophysiological mechanisms) using a *multi-method* research design (i.e., both observational and experimental research methods). The central hypothesis of this study is that discriminatory stress is associated with poor kidney functioning and two potential mechanisms leading to poor kidney functioning -- increased inflammation and blood pressure dysregulation-- among African Americans with CKD. Using a multi-method design, we plan to objectively test our central hypothesis by pursuing the following specific aims:

Objective 1. To examine associations between chronic stressors (i.e., discriminatory versus general), pathophysiological mechanisms (i.e., elevated inflammation and nocturnal blood

pressure), and **poor kidney functioning** (as measured by eGFR and proteinuria) among 100 African American patients (80 with a CKD diagnosis and estimated glomerular filtration rate [eGFR] ≥ 15 or < 90 ; 20 without a CKD diagnosis).

- ❖ Based on a cross-sectional research design, we hypothesize that chronic discriminatory stressors will be associated with poor kidney functioning independent of other chronic stressors as mediated by CKD-related inflammatory biomarkers and autonomic arousal.

Objective 2. To examine the impact of acute stressors (i.e., discriminatory versus general) on short-term changes in **CKD-related physiological processes** (i.e., increases in traditional and novel inflammatory markers and blood pressure reactivity) in patients from aim 1.

[figure not shown]

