- ❖ Utilizing an experimental research design will allow us to explore causal mechanisms through which discriminatory stress may contribute to CKD-related physiological processes. We hypothesize that discriminatory stressors will be more physiologically impactful than general stressors. Outcomes include several critical CKD-related inflammatory biomarkers (i.e., Monocyte Chemoattractant Protein-1 [MCP-1], Interleukin-6 [IL-6], and the novel soluble urokinase-type plasminogen activator receptor [suPAR]²⁶) and blood pressure reactivity assessed at multiple time points during the experimental manipulation.

It is anticipated that these aims will yield *outcomes* with great clinical and public health impact. First, we will refine methods to experimentally manipulate exposure to general and discriminatory stressors and assess their relationship to clinically important outcomes. Second, we will use novel inflammatory markers alongside the more standard ones to determine whether they mediate these relationships. Collectively, these outcomes are expected to have an important *positive impact* on the field of public health and the mission of NIDDK through the advancement of science-based information about CKD that can be disseminated for the purpose of improving health and quality of life.

III. Study Design

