This multi-method study will collect data from 100 African American patients (80 patients in stages 2, 3A, 3B, and 4 of CKD and 20 with no CKD diagnosis) utilizing both cross-sectional (aim 1) and experimental (aim 2) research designs (see Figure 1). The proposed methods were designed to maximize the robustness of the data while minimizing bias in study design, methodology, analysis, interpretation, and reporting. The use of validated instruments enhances the study's scientific rigor for aim 1. Random assignment to condition (for aim 2) eliminates selection bias as one potential threat to internal validity among others.²⁷ Additionally treating the two groups equivalently in terms of data collection methods and instrumentation improve internal validity by minimizing testing and instrumentation effects.²⁷ Detailed recruitment and data collection protocols further enhance the scientific rigor of the study because they ensure equal treatment of participants regardless of study condition. Finally, by intentionally studying patients along the continuum of CKD, we can explore whether there are "critical periods" in CKD progression where the relationships with stress are strongest.

Figure 1. Study Design

A. Organizational Structure

This study is funded by the National Institutes of Health (NIH), National Institute of Diabetes and Digestive and Kidney Diseases (NIDDK), and was developed by faculty in the Rollins School of Public Health. An internal medicine clinic within Emory University Hospital Midtown (at which Co-Investigator [name] currently serves as a practicing nephrologist) and the Georgia Clinical and Translational Science Alliance (GCTSA) (for which [name] serves as Co-Director) will serve as study sites. Additionally, study participants' bio-specimens will be analyzed at the Molecular Neuroimmunology Laboratory in the Department of Epidemiology at Emory. [name], who also serves as a Co-Investigator on this project, will oversee analyses of select blood samples. Outside laboratory resources will be used for processing and analyses of the remaining biospecimens.

B. Setting and location

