The first hypothesis is a meditational hypothesis. We recognize that Baron and Kenny⁶⁴ methods for testing mediation are among the most widely cited, but also acknowledge that there are convincing critiques of this approach such as the requirement that there be a significant direct effect of the independent variable on the outcome in order to proceed with meditational analyses.^{65,66} Thus, we will use meditational methods proposed by Zhao et al⁶⁵ that entail first running the Preacher and Hayes⁶⁷ SPSS syntax commands to generate “bootstrap” results for the indirect effect of chronic discriminatory stress (controlling for general stress) on each of the two kidney outcomes (eGFR and proteinuria) through the inflammatory pathway as measured by each of the proposed biomarkers (MCP-1, IL-6, suPAR). Bootstrapping relaxes assumptions about the shape of the sampling distribution of the indirect effect over repeated sampling from the population.⁶⁸ These analyses will control for relevant covariates. Next we will classify the type of mediation using the Zhao et al typology (complementary, competitive, indirect only, direct only, or non-mediation), and proceed with interpreting the findings in light of our hypotheses. We will consider using structural equation modeling as another technique recommended to test mediation.^{69,70}

The second hypothesis will entail use of a 2X3 ANOVA to simultaneously test the main effects of stress recall (race-related or not) (discriminatory stress vs. general stress) and data collection time point (rest, stress, and recovery) on each of the outcomes (i.e., each inflammatory biomarker and blood pressure), also controlling for the relevant covariates. This test provides a form of economy by examining multiple effects at a time, while also allowing us to study the interaction between study condition and time.⁷¹

C. Statistical Power

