The proposed proof-of-concept study is designed to generate effect sizes to inform a future power analysis and thereby establish the legitimacy of studying this topic in a subsequent large-scale clinical trial. Thus, it is not intended to achieve the level of power to demonstrate statistical significance as is common in larger studies. Nevertheless, regarding study aim 1, if we were to perform a multiple regression with 8 predictors that explain just 15% of the variance in a given outcome, we would achieve 84% power at $\alpha=.05$ (<http://danielsoper.com/statcalc3/calc.aspx?id=9>) at N=100. For aim 2, collecting data at multiple time points is one way to maximize power. If we just consider the two study groups (intervention and control) we would achieve power of .80 to detect a medium effect (.25) at $\alpha=.05$ with a sample of just 64 participants.⁷²

IX. Training of study team

All research staff maintains a current CITI, (Group 3 Social/Behavioral) certification. Proof of certifications has been uploaded for further review. Corresponding study team members (including members of the Georgia CTSA team and nurses within the Emory University Healthcare Nephrology clinic) will undergo study-specific training.

X. Plans for monitoring the study for safety

The Data and Safety Monitoring Plan (DSMP) outlined below will adhere to the protocol approved by Emory University. An IRB-approved written informed consent will be obtained from each participant at entry into the study; elements of informed consent will include: (a) having the participant review the study consent form; (b) having the investigator(s) or study staff meet with the participant to review the consent, confirm understanding, and answer any questions; and (c) once the investigator(s) or study staff are convinced that the protocol is understood and that there is agreement to participate, having the consent signed. The principal investigator (PI) will review all data collection documents weekly for completeness and accuracy of the data as well as protocol compliance. The PI will review this protocol on a continuing basis for participant safety and include the results of the review in annual progress reports submitted to the IRB and the NIH.

Patient Monitoring will be performed by the P.I., Co-Investigators, the Project Coordinator and medical staff present during the experimental manipulation. Also, H&P is required per the GCTSA protocol.

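### Aim 1 gives same-session indirect effects a mediation label, but the data cannot separate marker-to-kidney from kidney-to-marker; conclude in terms of indirect associations

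*Combined protocol and SAP*

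**What the plan says.** The Specific Aims and section II (Goals/Aims) present Aim 1 in these words: "Based on a cross-sectional research design, we hypothesize that chronic discriminatory stressors will be associated with poor kidney functioning". The same sentence goes on to name inflammatory biomarkers and autonomic arousal as the mediators.

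Under Day 2 in section III.E, the draw taken just before the stress task supplies both the inflammatory markers and a sample for eGFR. The urine specimen for proteinuria is collected at the same visit. The earlier eGFR in the medical chart is used only to fill the stage quotas.

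Section VIII.B estimates a bootstrap indirect effect of discriminatory stress, adjusted for general stress and covariates, for three biomarkers and two kidney outcomes (3 × 2 = 6 effects). Each is sorted into a five-way typology of mediation, and the authors then move on, "and proceed with interpreting the findings in light of our hypotheses". Section II says the study will use "novel inflammatory markers alongside the more standard ones to determine whether they mediate these relationships". Structural equation modelling is mentioned only as a further possible way to test mediation.

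No section describes a reversed-order model, a sensitivity analysis for direction, or a caution that the order of marker and kidney function is not identified.

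**The concern.** The label depends on a time order that the design does not supply. With stress, marker and kidney function observed once, the models stress → marker → kidney and stress → kidney → marker, each with a direct path, fit any set of three correlations equally well. Bootstrapping deals with the sampling distribution of the product of two coefficients. It says nothing about the direction of either path.

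The reverse path is a live possibility here. The markers were chosen partly because they are strongly associated with kidney disease, and the quotas deliberately spread the sample from no CKD diagnosis to stage 4. At stake is Aim 1's conclusion: it could name a pathway that the data cannot identify, and that pathway could shape the hypotheses of the larger study.

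**Working it through.** **The plan's own figure.** Section VIII.C supports Aim 1 with a power statement: "if we were to perform a multiple regression with 8 predictors that explain just 15% of the variance in a given outcome". With f² = .15/.85 = .176, noncentrality .176 × 100 = 17.6 and 8 and 91 degrees of freedom, power at α = .05 is 83.6%, against the stated 84%. The figure is reproduced. It concerns an overall R² and has no bearing on direction.

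**Inputs.** N = 100 and the bootstrap test of the indirect effect come from the plan. All correlations are assumptions, because the documents give none. Variables are standardised and normal, without covariates, so the correlations stand in for partial correlations in the adjusted model.

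Write S for stress, K for eGFR and M for a marker. The planned indirect effect is a × b, where a is the slope of M on S, and b is the slope of K on M given S.

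**Truth A: stress → eGFR → marker, with no marker effect on the kidney.**

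- a = r(SK) × r(KM)
- b = r(KM) × (1 − r(SK)²) / (1 − r(SK)² r(KM)²)
- At r(SK) = −.3 and r(KM) = −.5: a = .15; b = −.5 × .91 / .9775 = −.465; a × b = −.070.

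The statistical indirect effect is thus truly non-zero, although the marker does nothing to the kidney. The percentage of simulated studies whose 95% percentile interval excludes zero, per marker (800 data sets, 600 resamples), is:

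| Size of stress-eGFR correlation | eGFR-marker .3 | .5 | .7 |
|---|---|---|---|
| .1 | 4.5 | 9.2 | 12.6 |
| .2 | 8.5 | 18.2 | 31.1 |
| .3 | 10.9 | 33.8 | 56.4 |
| .4 | 19.8 | 53.1 | 79.4 |

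A separate run over eGFR-marker −.3 to −.6 gave 6-10%, 8-24%, 13-46% and 16-69% for the four rows. These are the ranges used in the conclusion. Where the two runs share a cell (eGFR-marker .3) they differ by at most 4 points (19.8 against 16). Monte Carlo error in the table is at most 1.96 × √(.25/800) = 3.5 points.

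With three markers tested against one outcome, and the markers independent given eGFR, the chance of at least one such label at .3/.5 is 68%. It is about 15% when stress and eGFR are unrelated, which is ordinary multiplicity.

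**Truth B: stress and poor kidney function each raise the marker, and stress is unrelated to the kidney.** Now b = r(KM) / (1 − a²). At a = .2 and r(KM) = −.5: b = −.5 / .96 = −.521 and a × b = −.104. Simulated percentages (1,000 data sets) for kidney-marker paths of .3/.5/.7 are:

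- stress path .2: 44.5/53.9/53.4
- stress path .3: 76.3/86.8/87.1

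**Would a reversed-order model (stress → kidney → marker) settle it?**

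- Truth A, stress-eGFR of .2 or more: among studies with the wrong label, the reversed effect is also significant in 74-100%.
- Truth B: the reversed effect is significant in only 4-7%. With stress paths of .2-.3, kidney-marker paths of .3-.5 and a stress-kidney correlation of 0 to .1, the planned effect alone is significant in 43-82% of studies.
- True mediation (stress path .2-.4, marker-to-kidney path .3-.7): the reversed effect is also significant in 9-80%.

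The reversed model's result depends on the sizes of the paths. It can display ambiguity, but it cannot establish direction.

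**The case against.** The strongest defence is that this is a proof-of-concept study. It says that it explores pathways and supplies effect sizes for a prospective successor, and section VIII.C disclaims confirmatory power. The hypothesis is phrased as an association, the design is openly called cross-sectional, and a prospective study could establish time order. All of this stands. It limits the consequence, so a reader should not infer that the follow-on study would necessarily rest on a wrong pathway. It does not remove the gap: the hypothesis also asserts mediation, and the planned output is a mediation type. Aim 2's randomisation bears on stressor to inflammation, not on inflammation to kidney.

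A second defence is that the larger percentages need large inputs. A stress-eGFR correlation of .3 is 9% of variance from one predictor, and .4 is 16%, which exceeds the 15% that section VIII.C assumes for eight predictors together. Adjustment for general stress and covariates could shrink the associations further. This also stands. The rows at .1 to .3 deserve most weight under truth A. Truth B needs no stress-kidney association at all, and the documents' own claim that the markers respond to acute stress makes it plausible.

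Two further inferences are tempting and unsupported. The first is that these percentages are an inflated type I error to be set against 5%. They are not: the statistical indirect effect is truly non-zero under both truths, and the error lies in its causal reading. The second is that a significant planned effect with a null reversed effect confirms direction. Truth B produces exactly that pattern.

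**Conclusion.** The concern holds in a conditional form. Section VIII.B assigns mediation types to effects whose direction the design cannot identify, and no text acknowledges it. With no marker effect on the kidney, a marker would be labelled a mediator in about 6-10%, 8-24%, 13-46% and 16-69% of studies at stress-eGFR correlations of -.1, -.2, -.3 and -.4 (eGFR-marker -.3 to -.6). The figure is about 45-86% if stress (path .2-.3) and poor kidney function each raise the marker independently.

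Reverse causation could therefore be reported as mediation, and at moderate associations often would be. A reader might infer that it would usually be so reported. The documents give no correlations from which to say that, and under truth A with a weak stress-kidney association it is uncommon. Covariates, quota sampling by stage, skewed markers and the second outcome were not modelled.

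This is a limit on what Aim 1 may claim and a cheap improvement to the plan. It is not a fault in the bootstrap test itself.

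**What to change.** In section VIII.B, and in the matching sentence of section II:

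1. Report Aim 1 results as indirect associations consistent with mediation, whatever any reversed model shows.
2. State that a mediation reading assumes no effect of kidney function on the markers, and that same-session data cannot test this.
3. Say that the typology label will not be used as evidence of a causal pathway when the follow-on study is planned.
4. Optionally, show the reversed-order model beside the planned one, with the same covariates and bootstrap, as a descriptive display of ambiguity. Attach no decision rule to it. In particular, do not reserve the statement that direction is unidentified for cases where both effects exclude zero.

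The cost is a more cautious Aim 1 conclusion and, if step 4 is used, six extra models (three markers by two outcomes) on data already collected.

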- **Biological data** in the form of blood and urine in order to assess kidney functioning and inflammation
- **Biological data** in the form of height, weight, and blood pressure to assess standard control variables (i.e., Body Mass Index) and blood pressure reactivity

Table 2 below lists the key constructs that will be measured, how they will be assessed, and the data source.

Table 2: Key constructs, measures, and data sources

Construct*	Measure	Data Source
Study Aim 1 (Chronic General and Discriminatory Stress)		
Chronic General Stress	Perceived Stress Scale, Financial stress, Neighborhood stress scales	Cross-sectional survey (CAPI)
Chronic Discriminatory Stress	Everyday discrimination, Major experiences of discrimination, Vicarious exposure to discrimination scales	Cross-sectional survey (CAPI)
Inflammation	MCP-1,, IL-6, suPAR ^{26,39}	Baseline blood draw
Autonomic arousal	Nocturnal blood pressure	ABPM
Kidney functioning	eGFR based on the abbreviated Modification of Diet in Renal Disease study equation ^{40,41}	Baseline blood draw

Kidney functioning	Proteinuria based on the albumin-creatinine ratio ⁴²	Baseline urine sample
Study Aim 2 (Acute General and Discriminatory Stress)		
Subjective ratings of distress	Subjective Units of Distress Scale (SUDS) ³²	Cross-sectional survey (SUDS)
Subjective ratings of recall distress	Cooper's Racism Recall Scale ³⁴	Cross-sectional survey
Inflammation	MCP-1, IL-6, suPAR ^{26,39}	Blood draw at 2 time points
Autonomic reactivity	Blood pressure	Blood pressure reading

Research Instruments and Assessment

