at that time; 4) how they felt at the time and 5) the most stressful/upsetting aspect of the experience. Patients will be given 2 minutes to prepare and 3 minutes to recount their experience for either the racial and non-racial stressful experience. This protocol has been used in other studies of African Americans³⁴ and is adapted from a widely used mental stress protocol used in studies of anger.^{62,63}

Subjective Ratings of Distress. In order to enhance the scientific rigor of this study, we will conduct a manipulation check to determine whether the experimental manipulation had its intended effect on study participants. Thus, subjective levels of distress will be measured immediately before and after the recall task. Using the Subjective Units of Distress Scale³² patients will be asked to rate their level of distress on a linear scale of 0 to 100, with 100 being the highest. Participants will also be asked to assess their level of stress directly related to reliving the stressful experience using an adapted version of Cooper's Racism Recall scale³⁴. Patients will rate their level of distress at the time of the event, and currently while thinking about the event on a linear scale of 0 to 10, with 10 being the highest.

- viii. **Inflammatory and Blood Pressure Reactivity.** Levels of inflammation will be measured at three time points during the experimental manipulation (immediately before the experimental manipulation, 45 minutes after the manipulation and 90 minutes after the manipulation) as shown in Figure 2. A description of the inflammatory markers is provided above under "Aim 1 Assessments". Systolic and Diastolic blood pressure will be assessed every 5 minutes during the rest and instruction period, every minute during the preparation and recall task, and every 5 minutes during recovery, as shown in Figure 2. Mean scores for rest, recall task, and recovery will be calculated by averaging the readings taken during each period. Blood pressure reactivity will be a change (or delta) score, calculated as the mean of the scores during the recall task minus the mean of the scores during rest, designed to represent the change in blood pressure induced by the recall task.

Overall Time Burden

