We will start by creating a data set that merges the survey data with all biometric data. Traditional data entry for the survey data will be unnecessary as data will be imported directly into SPSS from the REDCap software that houses the CAPI-questionnaire. Data will be cleaned, coded, and examined for any missing data or unlikely values. We will examine frequency distributions for all variables, with particular attention to variable ranges, missing values, and transforming variables as needed, depending on evidence of internal consistency within scales. Next, we will conduct exploratory analyses to determine whether participants with the different sequences (i.e. race-related recall first or second) differ on demographic, clinical, or behavioral variables. Specifically, we will use logistic models to regress recall sequence on all relevant variables. If significant differences are identified, we will conduct further analyses by stratifying by these particular variables and consider adjustment for these variables in our main analyses as described below.

B. Main Outcome Analyses

These analyses are driven by the two hypotheses stated above: (1) Chronic discriminatory stressors will be associated with poor kidney functioning independent of other chronic stressors

as mediated by CKD-related inflammatory biomarkers and autonomic arousal; (2) Discriminatory stressors will be more physiologically impactful than general stressors on critical CKD-related inflammatory biomarkers and blood pressure reactivity.

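### For Hypothesis 2 the plan names the recall main effect, which averages in a level measured before the recall, and does not say which term decides or supplies the effect size

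*Combined protocol and SAP*

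**What the plan says.** Section VIII.B states the second hypothesis as "Discriminatory stressors will be more physiologically impactful than general stressors on critical CKD-related inflammatory biomarkers and blood pressure reactivity". The analysis is a "2X3 ANOVA to simultaneously test the main effects of stress recall (race-related or not) (discriminatory stress vs. general stress) and data collection time point", with time levels "rest, stress, and recovery", run for each biomarker and for blood pressure with adjustment for relevant covariates. The interaction comes in a closing clause: the test offers economy "while also allowing us to study the interaction between study condition and time".

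The measurements are in section III.E, item viii. Biomarkers are drawn "immediately before the experimental manipulation, 45 minutes after the manipulation and 90 minutes after the manipulation". Blood pressure is averaged within rest, recall task and recovery, and a reactivity score is defined: "Blood pressure reactivity will be a change (or delta) score, calculated as the mean of the scores during the recall task minus" the rest mean. Section VIII.B does not tie a test to that score, and no change measure is defined for the biomarkers.

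Objective 2 (section II) concerns short-term changes, including increases in the markers. Sections II and VIII.C both say the study is meant to yield effect sizes for planning a later study.

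**The concern.** Each participant is randomised to one recall type. Before the recall the two arms have been treated alike, so no arm difference is expected at rest or at the pre-manipulation draw. A main effect of recall averages the arm difference over all three levels, including that one, so it answers a different question from the objective, which is about change.

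This is the study's only randomised comparison. If the named term is reported as the effect size, the difference after the recall is understated, and a real effect could look too small to pursue in the larger trial. The covariate wording does not prevent this: the list in section III.E, item vi, does not include the outcome's own pre-manipulation value.

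**Working it through.** **The plan's own figure.** Section VIII.C gives power .80 for a medium effect of .25 at two-sided α = .05 (sidedness assumed) with 64 participants, considering only the two groups. Reading .25 as Cohen's f, equal to d = 0.5 for two equal groups, a two-group ANOVA has power .50 at 64 in total, .70 at 100 and .80 at 128. The stated 64 therefore matches a per-group number. That is a separate matter; only d = 0.5 is carried forward.

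**Inputs.** N = 100 allocated 1:1, so about 50 per arm (section III.E, Day 2). Three time levels, the first before the recall (section III.E, item viii). True arm difference 0 at the first level and 0.5 SD afterwards. Assumptions not in the documents: SD 1 at each time and equal correlation ρ between times, at .3, .5, .7 and .8.

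**Estimate in outcome units.** The recall main effect is the mean of the three arm differences.

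- Sustained: (0 + 0.5 + 0.5)/3 = 0.33 SD, two thirds of 0.5.
- One later time only: (0 + 0.5 + 0)/3 = 0.17 SD, one third of 0.5.

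Neither result involves ρ. A baseline-adjusted or change-from-rest contrast at an affected time estimates the full 0.5.

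**Standardised estimate.** Dividing by the SD of the person mean, √((1+2ρ)/3), gives .46/.41/.37/.36 if sustained (91/82/75/72% of .50) and .23/.20/.19/.18 if at one time.

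**Power.** Formulas, with n = 50 per arm:

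- Main effect: variance of the person mean (1+2ρ)/3, noncentral t, 98 df.
- Baseline-adjusted contrast at one time: residual variance 1−ρ², 97 df.
- Change from rest at one time: variance 2(1−ρ), 98 df.
- Interaction: noncentral F(2,196), noncentrality 25 × Σ(dⱼ − d̄)²/(1−ρ). The sum is 0.167 for either pattern; at ρ = .5 this gives 25 × 0.167/0.5 = 8.3.

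| Test | ρ=.3 | .5 | .7 | .8 |
|---|---|---|---|---|
| Main effect, sustained | .62 | .52 | .45 | .43 |
| Main effect, one time | .20 | .17 | .15 | .14 |
| 2-df interaction, either pattern | .57 | .73 | .92 | .99 |
| Baseline-adjusted, affected time | .74 | .82 | .93 | .98 |
| Change from rest, affected time | .55 | .70 | .89 | .97 |
| Baseline-adjusted average of both later times, sustained | .91 | .94 | .98 | >.99 |
| The same, effect at one time | .38 | .42 | .54 | .68 |

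At lower correlation with a sustained effect, the main effect does better than the 2-df interaction: .68 against .51 at ρ = .2, and .65 against .54 at ρ = .25. The order reverses a little above .3.

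**The case against.** The strongest reply is that the right contrast is already in the model. The interaction is part of the planned ANOVA, Objective 2 speaks of change, and Hypothesis 2 names reactivity, which section III.E defines as recall minus rest. On that reading, blood pressure in section VIII.B is shorthand and the team would report change. Much of this stands: the dilution arises only if the main effect is the term used. But no section says it is not, it is the term the plan names, and the biomarkers have no defined change measure to fall back on.

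A second reply is that the study is expressly not powered for significance. That reduces the weight of the power figures, but not of the diluted estimate, since effect sizes are the stated product.

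Four stronger readings are tempting but not supported.

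- A reader might infer that the interaction is never examined. The plan does provide for studying it.
- A reader might infer that the main effect always has less power. With a sustained effect and correlation up to about .3, it has more than the 2-df interaction.
- A reader might set Table 2's "Blood draw at 2 time points" for Aim 2 inflammation against the three draws in section III.E. Table 2 lists a baseline draw under Aim 1, so the two can be the later draws.
- A reader might infer from readings taken "every 5 minutes during the rest and instruction period" that the rest mean already contains the effect. The text does not say which readings enter that mean or how long instruction lasts, and Figure 2, to which it refers, could not be read here. This is a point to clarify, and its size cannot be estimated.

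**Conclusion.** The concern holds: the term named for Hypothesis 2 is not the quantity the objective describes, and the deciding and reported contrast is left open. If the recall main effect is used, it estimates two thirds or one third of the arm difference after the recall. That rests only on the arms not differing before the recall, which randomisation gives in expectation. The power loss is less certain, because it depends on an assumed correlation, a 0.5 SD effect and the equal-correlation model. If a change from rest or a baseline-adjusted contrast is used instead, the dilution does not arise. This should be fixed before analysis.

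**What to change.** In section VIII.B, state that the recall main effect is neither the test nor the effect size for Hypothesis 2. Make the deciding and reported quantity a baseline-adjusted arm contrast:

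- recall-period mean systolic and diastolic pressure, each adjusted for its rest mean;
- each biomarker at 45 and 90 minutes, adjusted for its pre-manipulation value, with the deciding time, or the average of the two, named in advance.

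A prespecified 1-df change-from-rest contrast is an acceptable alternative. For blood pressure this is the reactivity score already defined; it is not the same test as the 2-df interaction. The interaction can be reported as an omnibus test.

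Two minor clarifications: say that the rest mean uses readings taken before the participant learns the recall type, and label the biomarker times pre, 45 and 90 minutes in place of rest, stress and recovery.

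The cost is a few sentences and possibly a different SPSS procedure, with no new data. The downside is that the contrast must be fixed before the data are seen. For the biomarkers, averaging the two times gains power if the effect lasts and loses it if the effect is confined to one of them.
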